Recently, we have developed 'The Colostomy Impact Score' (CI-score), which is a simple scoring system evaluating stoma-problems in patients with a permanent colostomy after rectal cancer surgery. It was based on direct patient-reported individual outcome measures concerned with various aspects of daily life with stoma, as mapped against overall HRQoL. 610 patients treated between 2001-2007, answered a 22-items basic stoma questionnaire and one anchor question addressing the overall stoma impact on HRQoL. Regression analyses identified 7 items/questions with significant impact on HRQoL, and each item/question was allocated a weighed scoring-value. The score comprises 7 items and has a sensitivity of 85,7% for detecting patients with significant impact on HRQoL.

This CI-score is currently available in Danish and English and was developed on a Danish population. We believe it to be a quick and reliable tool to screen patients for stoma-related negative impact on HRQoL. There is no doubt that there are significant cultural, social, religious, and demographic factors that can influence a patient's experience of life with a stoma. In addition to this, perception of an individual's HRQoL is known to differ between various populations [13], [14]. Therefore, before widespread uptake of the CI-score can be promulgated, studies on reliability and validity must be performed internationally across multiple patient populations.

This retrospective cohort study has three main aims: 1) To identify demographic and socioeconomic factors influencing stoma impact and HRQoL, 2) To assess reliability and to validate the translated and cross-cultural adapted CI score internationally in multiple different centres, across a variety of patient groups and across cultural, religious, socioeconomic and physical borders and 3) To investigate if differences in everyday stoma care and -costs across countries and cultures affect CI or HRQoL.

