*Content validity:* Comprehensiveness and relevance of the questions in the CI-score have been ensured with the way of the development of the CI-score with the starting point in a Basic Stoma Questionnaire developed by an expert group supplemented by patients ensuring that all possible factors affecting stoma function/impact was included before regression analysis lead to the seven weighed questions. After translation and cross-cultural adaptation face-validity of each translated CI-score will be assessed again by the collaborators before inclusion of patients.

*Construct validity:* This will be tested with hypothesis-testing. The following a priori formulated hypotheses on the construct validity will be tested:

- With a cut-off at 10 point the CI-score will have a sensitivity of at least 85% and a specificity of at least 50% of identifying patients with substantial colostomy impact as measured by the anchor questions (Anchor 1: poor/very poor satisfaction, remaining: Some/major impact).
- Patients with a CI-score of  $\geq 10$  have significant higher scores than patients with CI-score of  $< 10$  on all scales on the EORTC-QLQ-C30 questionnaire and this difference is clinically relevant in global health status, role functioning, social functioning and fatigue.
- Patients with a CI-score of  $\geq 10$  have significant higher scores than patients with CI-score of  $< 10$  on all scales on the EORTC-QLQ-CR29 and this difference is clinically relevant in stoma care problems.
- Patients with a CI-score of  $\geq 10$  have significant worse index value in the EQ-5D-L compared to patients with a CI-score of  $< 10$ . The sensitivity and specificity are expected to be comparable to when comparing to the anchor questions (hypothesis #1).
- The sensitivity and specificity are expected to be the same across all countries performing the validation.
- Men and women have the same relation between CI-score and HRQoL.
- If stoma care products confer a financial burden on the household the CI-score will show poorer correlation with HRQoL compared to patients where stoma care products do not confer a financial burden on the household.
- If the patients' religious affiliation or practice conflicts with having a colostomy, the CI-score will have a poorer correlation to HRQoL compared to patients who are not religious or if their religious practice does not conflict with having a stoma.

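### The cost and religion hypotheses compare only correlations, so they cannot show HRQoL that is worse by a constant amount at the same CI-score, and no named analysis holds the CI-score fixed

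*Combined protocol and SAP*

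**What the plan says.** Under Material and methods, Content validity, the protocol states: "Comprehensiveness and relevance of the questions in the CI-score have been ensured with the way of the development of the CI-score". It gives as the reason a process "ensuring that all possible factors affecting stoma function/impact was included before regression analysis lead to the seven weighed questions". The Background says that the score "was developed on a Danish population", from 610 patients and a 22-item questionnaire. It also says that "there are significant cultural, social, religious, and demographic factors that can influence a patient's experience of life with a stoma", and that validation across populations is needed before wide use.

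The one new content check follows translation and adaptation: "face-validity of each translated CI-score will be assessed again by the collaborators before inclusion of patients". Patients in the new countries are not mentioned.

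Under Construct validity, the seventh hypothesis reads "If stoma care products confer a financial burden on the household the CI-score will show poorer correlation with HRQoL compared to patients" without such a burden. The eighth makes the same kind of prediction for religious conflict. Further down the list, HRQoL itself is compared between patients with and without a cost burden, with and without access to a stoma nurse, and with and without need for help with care. Religious conflict has no such comparison.

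Statistical analysis works country by country and names only univariate regression, without listing covariates. The Objectives include the influence of religious and socioeconomic factors on CI-score and HRQoL.

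**The concern.** A seven-item score moved to new settings may lack a source of stoma impact that matters there. A natural form of that failure is a level shift: two patients have the same CI-score, but the one with the extra burden is worse off. The question to ask is therefore whether, at a given CI-score, HRQoL or the anchor is worse in exposed patients. The seventh and eighth hypotheses ask instead whether the CI-HRQoL association is weaker within the exposed group. The study could report no weakening of the correlation for cost or religion while the 10-point cut-off misses a larger share of the affected patients in those groups.

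**Working it through.** **1. What each planned check conditions on**

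| Check | Compares | CI-score held fixed? |
|---|---|---|
| Hypotheses 7 and 8 (cost, religion) | CI-HRQoL correlation between groups | No; blind to level |
| HRQoL by cost burden | Mean HRQoL | No |
| HRQoL by religious conflict | Not listed | – |
| Hypotheses 1 and 5, sensitivity by country | Whole country | Not split by exposure |
| Univariate regression | One covariate at a time | No |

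**2. Correlation and a constant shift.** If every exposed patient loses d points, Corr(X, Y − d) = Cov(X, Y) / (SD(X) × SD(Y)) = Corr(X, Y). The slope is also unchanged. This needs no distributional assumption.

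**3. The unadjusted cost comparison.** The protocol's SD is 22 and its minimal clinical difference 10 points. (These reproduce its sample size of 206: 103 per group gives 90.1% power with the t-distribution at two-sided 5%. Sidedness and power are assumed, because they are not stated.) Assume a correlation of −0.5. The HRQoL slope is then −0.5 × 22 = −11 points per SD of CI-score.
- Cost acts only through the CI-score: exposed patients score 10/11 SD higher. Unadjusted difference −11 × 10/11 = −10; difference at equal CI-score 0.
- Cost adds impact at the same CI-score: unadjusted difference −10; difference at equal CI-score −10.

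The planned comparison gives the same answer in both cases.

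**4. Rejection rates, simulated.** Assumptions: correlation −0.5, 250 × 0.8 = 200 evaluable patients, exposure unrelated to CI-score, 10-point loss at equal CI-score.

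| Share exposed | Correlation comparison | Unadjusted HRQoL | HRQoL adjusted for CI-score |
|---|---|---|---|
| 20% | 0.050 | 0.73 | 0.84 |
| 30% | 0.050 | 0.84 | 0.92 |
| 50% | 0.047 | 0.90 | 0.96 |

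The correlation comparison rejects only at its false-positive rate.

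**5. Effect on sensitivity.** Assumptions not in the documents: CI-score and impact are bivariate normal with correlation r; 25% are anchor-positive, so the anchor threshold is 0.674; the exposed have 0.5 SD more impact, unrelated to CI-score. The cut-off c solves P(X > c, Y > 0.674) / 0.25 = 0.857, using the Background's 85.7% sensitivity. In exposed patients the threshold becomes 0.674 − 0.5 = 0.174, so 43% are anchor-positive and sensitivity is P(X > c, Y > 0.174) / 0.431.

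| r | c | Sensitivity, unexposed | Sensitivity, exposed | Specificity, unexposed to exposed |
|---|---|---|---|---|
| 0.5 | −0.324 | 85.7% | 80.4% | 0.45 to 0.51 |
| 0.6 | −0.145 | 85.7% | 78.6% | 0.54 to 0.62 |
| 0.7 | 0.049 | 85.7% | 76.2% | 0.65 to 0.73 |

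With the protocol's 10 points over SD 22 (0.45 SD), sensitivity in the exposed is 80.9%, 79.3% and 77.2%.

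**6. What the country figures would show.** At r = 0.6 with a fraction f exposed, country sensitivity is [f × 0.431 × 0.786 + (1 − f) × 0.25 × 0.857] / [f × 0.431 + (1 − f) × 0.25]. This gives 83.6%, 82.7% and 81.2% for f = 20%, 30% and 50%, against the 85% of hypothesis 1.

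**The case against.** A reader might infer that impact from cost or religion would go undetected altogether. The documents do not support that. HRQoL is compared by cost burden, nurse access and need for help, and step 4 puts the unadjusted comparison at 0.73 to 0.90 for a 10-point loss. For cost, what is missing is attribution, not detection. Hypotheses 1 and 5 could also show a modest loss of sensitivity by country, though not its cause or in whom.

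A reader might also infer that the score is simply taken as complete for all 15 countries. The Background asks for validation before wide use, and face validity is reassessed after adaptation, although by collaborators only. The two hypotheses predict weaker correlation; they do not state that cost or religion adds impact.

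Other objections stand in part. If the added impact varies between exposed patients, it adds variance and weakens the correlation, which is the pattern that these hypotheses look for. The blindness is to a roughly constant shift. If burden also raises the CI-score, the sensitivity loss shrinks, and specificity rises in the same model. Finally, worse global health at equal CI-score may reflect deprivation or general ill-health, so it does not by itself show that a stoma item is missing.

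None of this supplies an analysis at fixed CI-score, or an HRQoL-level hypothesis for religious conflict.

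**Conclusion.** The point holds as a gap in what the tests can separate. Hypotheses 7 and 8 cannot show a constant shift at equal CI-score; that is algebra. For cost, the plan would probably find a difference without being able to interpret it. For religion, which the Objectives name, no listed hypothesis tests the level at all; the univariate regressions might touch it, but their covariates are unnamed and they do not condition on CI-score. The illustrated size is a loss of about 5 to 9 percentage points of sensitivity in exposed patients (85.7% to between 80.4% and 76.2%), with a gain in specificity. Those figures rest on the latent-normal model, the 25% anchor-positive rate, the assumed correlations and a 0.5 SD shift unrelated to CI-score.

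**What to change.** For hypotheses 7 and 8, add a regression on CI-score, exposure and their interaction, by country and pooled with country strata. Use the anchor group as the main outcome and QLQ-C30 global health status as supportive. Centre the CI-score at the 10-point cut-off so that the exposure effect is read at a stated score, and report it with a 95% CI. Report sensitivity and specificity by exposure group.

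State the interpretation in advance. A shift on the anchor suggests possible stoma impact that the score does not capture. A shift on global health is supportive only, because deprivation or ill-health may explain it. Set no automatic rule that a 10-point shift makes the score not comprehensive.

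In Content validity, limit the comprehensiveness statement to the Danish development population.

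The cost is a few extra regressions on data already collected, with no further patient contact. Country-level estimates will be imprecise where few patients are exposed, which is the reason for the pooled analysis.

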#### Data analysis:

Construct validity: Convergent validity will be studied by testing the CI-score on APE/Hartmann-patients against two measures of HRQoL; the anchor-questions assessing the overall stoma-impact on HRQoL, the EORTC QLQ C30 questionnaire version 3.0 and the EORTC QLQ CR29. Construct validity will furthermore be assessed by hypothesis-testing assessing the direction and magnitude of the expected correlations. Test-retest reliability will be studied on a subgroup in all included

countries. Also, we will include questions on background demographics, socioeconomic status, everyday stoma care and -costs thereby enabling investigation of the practical and economic aspect of living with a stoma varying from country to country.

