#### Statistical analysis:

Statistical analysis will be performed separately for each country.

The correlations between total CI-score, anchor questions and the EORTC questionnaire results will be calculated for all participating patients according to the guidelines for the scores. For each CI-score group (minor CI/major CI) the mean EORTC QLQ C30-score will be calculated, testing the overall difference of impact on HRQoL between the CI-score groups.

Using the anchor-questions, the patients are divided into two HRQoL groups of those reporting no/minor or some/major impact on HRQoL. Relationship between CI-score and HRQoL group will be illustrated in box-plot for each country, where we expect statistically significant differences in median CI-score between the two HRQoL groups. Differences will be tested by Mann-Whitney U test. A contingency 2 by 2 table will be used to assess the degree of agreement between the two CI-score groups and the two HRQoL groups. Based on this, the sensitivity for the score will be calculated for each country. The added questions about irrigation and stoma-bag change frequency will be compared country-wise. Univariate regression analysis, descriptive analysis and estimation of impact on HRQoL will be performed. Test-retest reliability will be evaluated using Intraclass Correlation Coefficient and Cohens' Kappa.

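### Hypothesis 2 predicts higher QLQ-C30 scores for the worse-off CI-score group, which is the wrong direction on three of its four named scales if they are scored as their names suggest

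*Combined protocol and SAP*

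**What the plan says.** Under Material and methods, the construct-validity paragraph opens its list with "The following a priori formulated hypotheses on the construct validity will be tested". The second item says that patients at or above the cut-off of 10 "have significant higher scores than patients with CI-score of" less than 10, and that this applies "on all scales on the EORTC-QLQ-C30 questionnaire and this difference is clinically relevant in global health status, role functioning, social functioning and fatigue".

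Three other statements show which group is meant to be worse off:

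- The Background presents the CI-score as a "quick and reliable tool to screen patients for stoma-related negative impact on HRQoL".
- Hypothesis 1 uses the 10-point cut-off for "identifying patients with substantial colostomy impact as measured by the anchor questions".
- Hypothesis 4 predicts for the same group a "significant worse index value in the EQ-5D-L compared to patients with a CI-score of" less than 10.

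On scoring, the Statistical analysis section says only that the results "will be calculated for all participating patients according to the guidelines for the scores". It gives no direction for any QLQ-C30 scale and mentions no reversal or recoding.

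**The concern.** Hypothesis 2 uses one word, *higher*, for every QLQ-C30 scale. Two of the four scales it names measure functioning, one measures global health and one measures a symptom. For a group expected to do worse, *higher* is the right prediction on all four only if all four are scored so that a larger number means a worse state. The protocol does not say that they are.

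What is at stake is whether a pre-specified validity criterion can be read. The Data analysis section says that construct validity is judged by "hypothesis-testing assessing the direction and magnitude of the expected correlations", so direction is meant to count, although that sentence speaks of correlations and not of group differences. Because the analysis is done separately in each country, each national team would have to interpret the criterion. If the meaning is settled only after the data are seen, the criterion is no longer clearly a priori.

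**Working it through.** **Does the sample-size paragraph settle the direction?** It is the only place that gives an EORTC value by CI-score group. The inputs there are a mean of 72 in the major CI group, SD 22, minimal clinical difference 10, alpha 0.05 and 206 patients. Power, sidedness and allocation are not stated.

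Assuming 90% power, a two-sided test and equal groups, the normal approximation gives per group

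n = 2 × (1.960 + 1.282)² × 22² / 10² = 2 × 10.51 × 4.84 ≈ 101.7, so 102 per group and 204 in total.

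The t-based calculation with the same inputs gives 103 per group, 206 in total, which is the protocol's figure. The difference enters as a square, so its sign does not matter. The paragraph does not name the scale and gives no mean for the minor group. With a 10-point difference, the minor group would be at 82 if higher is better (72 + 10) or at 62 if higher is worse (72 − 10), and both give the same N. The paragraph therefore does not show the scoring direction.

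**Direction, scale by scale.** The group at 10 or more is expected to be worse off (Background, hypotheses 1 and 4). Hypothesis 2 predicts *higher* on each scale. The table shows the direction that a worse-off group should have under three scoring assumptions.

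| Named scale | A: scored as the name suggests | B: higher = worse on all | C: higher = better on all |
|---|---|---|---|
| Global health status | lower (mismatch) | higher (match) | lower (mismatch) |
| Role functioning | lower (mismatch) | higher (match) | lower (mismatch) |
| Social functioning | lower (mismatch) | higher (match) | lower (mismatch) |
| Fatigue | higher (match) | higher (match) | lower (mismatch) |
| **Mismatches with *higher*** | **3 of 4** | **0 of 4** | **4 of 4** |

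Assumption A rests on the scale names alone. Only B makes hypothesis 2 correct as written, and the protocol states neither B nor a recoding that would produce it.

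**Hypothesis 3.** It uses the same wording for all QLQ-CR29 scales. The only scale it names is stoma care problems, where by its name higher means worse, so *higher* fits. No error can be shown there from the protocol.

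**What depends on the word.** The Statistical analysis section plans a mean QLQ-C30 score per CI-score group and a test of the overall difference between the groups, with no direction attached. The Mann-Whitney test and the two-by-two table use the anchor questions. None of these calculations changes.

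**The case against.** The strongest objection is that the protocol does not contain the fact on which the error depends. It leaves scoring to the instruments' guidelines, and a scale name is not a scoring rule; global health status in particular names a construct and not a direction. Hypothesis 2 also cites the development study, whose convention cannot be checked here. The range above includes zero mismatches, so what the protocol shows for certain is an ambiguity. This stands, and it is why the count of three is conditional.

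The second objection is that nobody would be misled. Hypothesis 4 says *worse*, the later hypotheses speak of inferior or better quality of life, the planned group test has no direction, and no rule counts confirmed hypotheses or rejects the score when one fails. This also stands, and it limits the consequence to the reading of one criterion.

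Neither objection removes the point. The text is correct only under a convention that the protocol does not state. Under the ordinary reading of the scale names, a stated a priori prediction points the wrong way. Clear intent makes the correction easy, but the criterion still needs correcting before it is tested.

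**Conclusion.** The concern holds, as a minor one. Hypothesis 2 gives one direction for scales that, by their names, run in opposite directions. If they are scored as named, the prediction is wrong on 3 of the 4 named scales; the range over scoring assumptions is 0 to 4 of 4. Under the first reading, a CI-score that performs as intended would contradict the literal criterion on global health, role functioning and social functioning, and meet it on fatigue.

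The conclusion rests on one assumption (direction taken from the scale names) and one reading that the protocol supports (patients at 10 or more are the worse-off group). No bias, loss of power or effect on the sample size is claimed.

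**What to change.** Before analysis:

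1. In hypothesis 2, replace *higher scores* with *worse scores*. Spell this out as lower on global health and functioning scales and higher on symptom scales, once the sponsor has confirmed that this is how the scales are scored.
2. Add one line to the Statistical analysis section stating the scoring direction used for the QLQ-C30 and whether any scale is recoded.
3. Optionally, use the same wording in hypothesis 3, for consistency only.

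The cost is one word and one line of text (plus the same word in hypothesis 3 if wanted). Data collection, design and sample size do not change. Making the correction before the data are examined keeps the criterion a priori.

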#### **Material and methods:**

International validation will be conducted as a retrospective cohort study. Local health care professionals will identify includable patients and register relevant clinical information on each patient from the hospital chart. Most centres will include patients from national or regional databases, some will however include conveniently if a database is not available. Our international collaborators will be responsible for sending out and collecting the questionnaires and returning the completed questionnaires to the undersigned. In countries with sufficient internet accessibility and -infrastructure the data collection will be web based i.e. patients are sent a link to the redcap-database for them to enter their answers directly. Some centres will employ paper versions of the questionnaires. In areas with substantial number of illiterates investigator led interviews can be performed.

**Inclusion criteria:** Patients who were operated with curative intent for rectal cancer with APE, Hartmann's procedure or pelvic exenteration will be included retrospectively aiming at 250 patients from each of the participating countries. This number is based on a calculation of strength based on the results from the development of the CI-score. (mean EORTC score in the major CI-group: 72. SD: 22. Minimal clinical difference: 10 points. Alpha: 0,05 STATA => sample size 206 patients. Expected dropout: 20%). Accessibility to cohorts of interest may differ between countries. Therefore, number of patients and mode of contact to patients should be agreed by the local investigation and the steering group in the planning of the data collection and included as individual amendment to the final protocol. In Denmark patients operated from January 1st 2001 to December 31st 2016 will be included.

**Exclusion criteria:** Age less than 18 years, known disseminated or recurrent disease, mental dementia and the inability to understand the actual language.

As the CI-score is a construct based on a formative model, statistical analysis based on the Classical

Test Theory (CCT) and Item Response Theory (IRT) cannot be applied. However, the following aspects of validity and reliability from the COSMIN checklist can and will be evaluated:

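### Hypotheses 2 and 3 require significance on every EORTC scale, but 206 patients matches power for one scale, so a working CI-score can miss them as worded

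*Combined protocol and SAP*

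**What the plan says.** Under Material and methods, the construct-validity paragraph lists hypotheses formulated in advance. The second and third (hypotheses 2 and 3 here) compare patients with a CI-score of 10 or more with those below 10.

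- Hypothesis 2 expects a significant difference "on all scales on the EORTC-QLQ-C30 questionnaire and this difference is clinically relevant in global health status"; the sentence then also names role functioning, social functioning and fatigue.
- Hypothesis 3 expects a significant difference "on all scales on the EORTC-QLQ-CR29 and this difference is clinically relevant in stoma care problems".

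The sample size stands in the inclusion-criteria paragraph of the same section. The inputs are "mean EORTC score in the major CI-group: 72. SD: 22", then "Minimal clinical difference: 10 points", then "Alpha: 0,05 STATA => sample size 206 patients", with 20% dropout and the study "aiming at 250 patients from each of the participating countries". The source is given as "This number is based on a calculation of strength based on the results from the development of the CI-score". Power, sidedness, the split between the two groups and the EORTC scale concerned are not stated.

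The Statistical analysis section has each country analysed on its own. On this comparison it says "For each CI-score group (minor CI/major CI) the mean EORTC QLQ C30-score will be calculated", to test an overall difference in impact between the groups. No section says when a hypothesis counts as confirmed, allows partial confirmation, or defines how clinical relevance is judged.

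**The concern.** Each hypothesis is a conjunction. One non-significant scale, or one named scale without a relevant difference, and the hypothesis as written is not met. Every country faces that test with about 200 evaluable patients, while the only calculation in the plan concerns a single difference in means.

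The plan expects clinical relevance on only some scales. Smaller differences on the others are therefore plausible, and there the power per scale drops quickly.

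At stake is how the validation reads. A country could report two of its advance hypotheses as unmet although the score separates patients as intended. Alternatively, the result could be rescued by deciding afterwards which scales matter, which undoes the purpose of stating hypotheses in advance.

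**Working it through.** **Inputs from the plan.** Difference 10, SD 22, alpha 0.05, 206 patients, target 250, dropout 20%.

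**Assumptions.** Two-sided test; equal groups; SD 22 on every scale; 15 scales unless stated; a common correlation of 0 to 0.7 between the scale differences; relevance read as an observed difference of at least 10. None of these is in the documents.

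**Reproducing 206.** n per group = 2(1.960 + 1.282)² × 22² / 10² = 101.7, so 102. The t-based version gives 103, total 206, exactly the stated figure. With 80% power the total is 152 to 154, which does not match. One-sided 95% power gives 210 to 212, which is near but not exact. So 206 is about 90% power for one scale, with the 90% inferred.

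**Evaluable patients.** 250 × 0.8 = 200, or 100 per group. SE = 22 × √(2/100) = 3.11. The 95% half-width is 1.97 × 3.11 = 6.1.

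**Power for one scale, 100 per group (noncentral t).**

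| True difference | Power |
|---|---|
| 10 | 0.892 |
| 7 | 0.610 |
| 5 | 0.359 |

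A 30/70 split of 206 lowers power at 10 points from 0.90 to 0.85.

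**Joint rule for hypothesis 2, 15 scales, 100 per group.** The lower figures assume independence and can be checked by hand. The upper ones, at correlation 0.7, come from simulating equicorrelated normal differences.

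- *Every scale at 10, significance only.* 0.892^15 = 0.18, rising to 0.63.
- *Four named scales at 15, the other 11 at 7.5, full rule.* A named scale shows at least 10 with probability Φ(5/3.11) = 0.946, and all four with 0.946⁴ = 0.80. Power at 7.5 is 0.67, and 0.67^11 = 0.012. The product is 0.01, rising to 0.32.
- *All scales at 15, full rule.* Power at 15 is 0.998, so 0.998^11 × 0.80 = 0.78, rising to 0.87.
- *Named scales at exactly 10, relevance only.* 0.5⁴ = 0.06, rising to 0.27.

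With 8 scales all at 10 and 103 per group, all-scale significance is 0.44 to 0.72.

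**Joint rule for hypothesis 3** (one named scale, 5 to 20 scales, correlation 0 to 0.7, 103 per group). The full rule is met 0.07 to 0.48 of the time with every scale at 10, and 0.00 to 0.47 with the named scale at 15 and the rest at 7.5. With all scales at 15, 100 per group and independence, 20 scales give 0.946 × 0.998^19, about 0.91.

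**The case against.** A reader might infer that a valid score would usually fail these hypotheses. The documents do not support that as a general statement. The expected differences come from the cited development study and are not reproduced in the plan. Naming some scales as clinically relevant does not say that the others fall below 10. If every scale differs by 15, both hypotheses are met most of the time.

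A reader might also infer that 206 fails the hypotheses it was calculated for. The plan does not tie 206 to hypotheses 2 or 3. The overall comparison in the Statistical analysis section is close to what 206 does size.

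The 50% chance of observing at least 10 when the truth is exactly 10 is a property of any threshold judged at its own value, and the plan does not place the truth there. Nor does the plan draw any conclusion about the score from one unmet hypothesis; these are two in a long list. Finally, requiring every scale to be significant does not inflate type I error.

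These objections limit the size of the point. They do not remove it: the wording is still all scales, nothing elsewhere relaxes it, and no joint power is given.

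**Conclusion.** The point holds in conditional form. Hypotheses 2 and 3 are joint requirements applied country by country, and the stated sample size corresponds to about 90% power for one scale at 10 points. A working score can miss the rule as worded unless differences are well above 10 on nearly all scales.

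The size depends on unknowns. For hypothesis 2 with 15 scales, the chance of meeting the full rule runs from 0.01 to 0.32 in one plausible pattern of differences and from 0.78 to 0.87 in a more favourable one. The conclusion rests on the assumed scale counts and correlations, on SD 22 for every scale, on equal groups, and on reading relevance as an observed difference of at least 10. What fails is the hypothesis as worded; the documents attach no further consequence to it.

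**What to change.** - Judge hypothesis 2 on fatigue, global health status, and role and social functioning, and hypothesis 3 on stoma care problems, each scale on its own.
- Report every other C30 and CR29 scale as a mean difference with a 95% confidence interval and no pass or fail.
- Read relevance from the confidence interval against the plan's own 10 points: shown if the whole interval is at or above 10, refuted if it is wholly below 10, otherwise inconclusive, with the estimate and interval reported. Asking for an observed difference of at least 10 and an interval excluding 0 would not help: with a half-width of 6.1, the first condition already implies the second.
- State beside 206 that it gives about 90% power to detect a non-zero difference on one scale if the true difference is 10 points, and not for the joint claim. Confirm the power, the sidedness and the scale used.

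The cost is rewording two hypotheses and one sample-size sentence; no patients or data are added. The headline claim becomes narrower, and more relevance results will be inconclusive. Showing relevance needs an observed difference of at least 10 + 6.1 = 16.1; at a true 15 that has probability 1 − Φ((16.1 − 15)/3.11), about 0.36.

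Keeping the joint wording and sizing for it would cost far more. For significance alone on 15 scales, each at a true 10 points, 90% joint power needs about 320 to 384 evaluable patients per country (correlation 0.7 to 0).
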